4. STUDY POPULATION

4.1 Population (base)

4.2 Inclusion criteria

In order to be eligible to participate in this study, a subject must meet all of the following criteria:

All patients treated in the participating FACT teams and for patients treated at the LVB-P department of the GGZ Oost Brabant or the ORO foundation.

4.3 Exclusion criteria

A potential subject who meets any of the following criteria will be excluded from participation in this study:

If patients do not have sufficient command of the Dutch language or cannot concentrate for 20 minutes, the instruments are not taken.

4.4 Sample size calculation

The number of new registrations for FACT teams is between 30 and 40 per year. With a minimum of three participating FACT teams, there are approximately 100 new patients per year. In the 2.5 years of the planned data collection, there will be 250 new patients. Based on the information that approximately 40% of FACT patients function at the level of mild intellectual disability, we can include at least 150 patients. A very substantial part could refuse to participate in order to obtain the required 40 patients for the validity study.

The SumID-Q is administered at least 20 times a year within the various parts of the LVB-P department (ambulatory, part-time, clinic). Most administrations take place at the clinic, where SumID-Q administration is standard of care at the start of clinical admission. ORO also uses the SumID-Q more than ten times a year. The required 40 patients seems achievable within the period of data collection.

For both groups, we stop data collection at 100 participating patients.

5. TREATMENT OF SUBJECTS

N.a. because this is an observational study.

METHODS

5.1 Study parameters/endpoints

5.1.1 Main study parameter/endpoint

Problematic substance use

5.1.2 Secondary study parameters/endpoints (if applicable)

Quality of Life

Mental complaints

5.2 Randomisation, blinding and treatment allocation

n.a.

5.3 Study procedures

Objective 1:

The validation study of the TAPS was incorporated in a broader comprehensive screening and assessment procedure that is standard care in FACT teams in this mental healthcare institute.

All new patients were screened on intellectual disabilities, trauma-related symptoms and substance use problems. Actual psychiatric symptoms, quality of life, phase of recovery and the burden of care for relatives of the patient were also mapped. This screening and assessment consisted of one test, four self-report questionnaires for the patient, one questionnaire for relatives and one questionnaire for the caregiver. The TAPS-tool was used for screening and brief assessment of substance use problems. Only when a patient was incapable of concentrating for more than 15 minutes, when the Dutch language was a problem or when there was almost no cooperation for the FACT treatment at all, the screening and assessment was omitted.

Psychologists or case managers were the assessors. They invite the patient for an appointment to take the test and fill out the questionnaires together at home or at the office. The screening on possible intellectual disabilities was done first. There was no fixed order for the other parts.

For the validation of the TAPS two elements were added to the standard procedure: First, the assessor also took the parts of the MATE necessary to investigate the severity of the addiction (module 1, 4, and Q1; see description of the MATE above). Second, after completing the TAPS and the MATE, but before the scoring of it, the assessor also rated the severity of the substance use problems on a five-point Likert

scale by answering the following question: "I rate the addiction problem of the client as...". Possible answers were: absent, mild, moderate, severe, very severe .

Participants were invited by telephone for the regular appointment that was scheduled at least one day later. During this telephone conversation, information was given about the validation study of the TAPS and patients were asked if they want to think about voluntarily participation. During the appointment, the information about the validation study was reviewed again, any additional questions from the patients were answered and when the patient agreed for participation, informed consent was signed. Patients signed informed consent to use the answers of the TAPS and MATE and background information (age, gender, diagnosis, medication, level of education) anonymously for this scientific purpose.

To investigate research objective 1, the following measuring instruments are used:

TAPS:

Tobacco, Alcohol, Prescription medication and other Substances-tool.

The TAPS-tool is a 2-phase screening instrument to detect substance use problems which can be used as an interview or as a self-administered questionnaire. According to McNeely et al., the diagnostic characteristics of both ways are similar (McNeely et al., 2016).

The TAPS-1 (screener) pretends to detect unhealthy substance use in the past year quickly and is based on NIDA's quickscreen. It contains of four multiple choice questions where the patient answers how often they used tobacco, alcohol, other drugs, and prescription medication in te past year on a five point Likert-scale.

Possible answers are: never, less than monthly, monthly, weekly, daily or almost daily. For tobacco and drugs, a positive score is given when there is any use in the past year. For alcohol a positive score is given when someone drinks more than 4 (women) or 5 (men) drinks containing alcohol a day. For medication, a positive score is obtained when someone uses prescription medication in a higher dose, or uses medication from someone else or medication without prescription. If there is a positive score on any of the sections, the TAPS-2 is assessed (see below). Dus de TAPS-1 levert geen scores op zichzelf op, maar de scores dienen ertoe om te beslissen of je doorgaat met de TAPS 2 of niet? For the TAPS-1, the optimal cut-off points for the detection of a possible substance use disorder (SUD) are: For tobacco and alcohol a frequency of monthly use was a predictor for SUD (sensitivity = 0.92 and 0.71, specificity = 0.80 and 0.85, AUC = 0.86 and 0.78, respectively) and for illicit drugs and prescription medication misuse any reported use was suspect for SUD (sensitivity = 0.93 and 0.89, specificity = 0.85 and 0.91, AUC = 0.89 and 0.90, respectively).

(Gryczynski et al., 2017)

TAPS-2 (brief risk assessment) is based on the ASSIST-lite (Alcohol, Smoking and Substance Involvement Screening Test) which is developed by the World Health Organization (Ali, Meena, Eastwood, Richards, & Marsden, 2013). The ASSIST has a

good test-retest reliability: substance risk scores from two administrations within 1-4 weeks has excellent concordance (90–98%) and a high correlation (ICC 0.90–0.97) for tobacco, alcohol, and drugs (McNeely et al., 2014). The ASSIST-Lite (a shortened version of the ASSIST) has a single factor structure on which all substances loaded (eigenvalue range, 2.42–3.81). It also has a consistent pattern of positive loadings on this factor (all ≥ 0.303) (Ali et al., 2013). For the TAPS-2, only ADHD medication and questions about the failure to reduce or stop the use of marihuana, amphetamines and anxiolytics have been added to the ASSIST-Lite. There are nine categories on the TAPS-2: tobacco, alcohol, marihuana, stimulant drugs, opiates, anxiolytic medication, ADHD medication and 'other substances'. Only the elements with a positive score on the TAPS-1 are further assessed. For every category, the assessment with the TAPS-2 contains the usage for the last 3 months and two or three additional questions which can detect unhealthy use. For scoring both the use for the last 3 months and an affirmative answer on each of the additional questions lead to one point. A total score is calculated for each of the categories separately by adding the positive answers together. A total score of +2 per category induces a risk of a substance use disorder and indicates more assessment. Investigation of the TAPS-2 has been done by a comparison with the Composite International Diagnostic Interview (CIDI). Problematic use (with a cut off score of +1) for tobacco has a sensitivity of 0.93 and specificity of 0.87. Alcohol has a sensitivity of 0.74 and specificity of 0.79. For problematic use of illicit and prescription drugs, sensitivity ranges from 0.82 for marijuana to 0.63 for sedatives, and specificity is 0.93 or higher. For identifying any SUD, sensitivity was lower, but a cut off score of +2 greatly increases the likelihood of having a SUD as measured by the CIDI (McNeely et al., 2016).

HoNOS:

The course of the complaints is mapped out annually using the HoNOS (Health of the Nation Scale). This is an observation list that is completed by the practitioner. The outcome of the HoNOS reflects the mental and social functioning of a client in mental health care at a given moment. The HoNOS can be completed at several moments before, during or after a treatment, so that the change in complaints is mapped out. The aim of the HoNOS is therefore to evaluate the treatment or supervision. The score for the 12 items that make up the instrument always ranges from 0 (no problem) to 4 (very serious problem). These are issues that have occurred in the past two weeks. Psychometric properties of the HoNOS are satisfactory to good (Mulder et al., 2004).

MANSA:

The quality of life, as experienced by the patient, is mapped with the MANSA: the Manchester abbreviated quality of life measure (Van Nieuwenhuizen, Schene & Koeter, 2000), the 16 item version. The MANSA is a multidimensional questionnaire

designed to assess quality of life. The closed questions refer to job satisfaction, housing, general health and social relationships.

MATE:

MATE is the Dutch abbreviation of “Measurement of Addiction for Triage and Evaluation”. It is an instrument, developed in Europe to determine patient characteristics for the indication of care for people with addiction problems on a valid and reliable way. The MATE has ten modules (eight interview modules and two self-report questionnaires) which take about one hour to assess totally. These modules are: 1. substance use, 2. substance abuse and dependence, 3. craving, 4. depression, anxiety and stress, 5. psychotic symptoms, suicidality and current psychiatric treatment, 6. personality disorders, 7. physical complaints and symptoms 8. personal and societal functioning, 9. environmental factors influencing recovery, and 10. history of substance abuse treatment. The MATE comprises a set of existing, well-developed and widely accepted instruments to investigate the ten module-themes: for example the CIDI (Composite International Diagnostic Interview) to investigate ICD criteria, the DASS (Depression Anxiety Stress Scales) to investigate depression and anxiety, and the SAPA (Standard Assessment of Personality Abbreviated scale) to investigate personality disorders.

The modular design of the MATE can be used in a flexible way which gives service delivery institutions the freedom to select their intake and evaluation tools individually from the MATE modules. The original Dutch version is translated into English, German and Spanish.

The factor structure of the ICF-related modules has revealed a three-factor model with an acceptable fit. Inter-rater reliability ranges between 0.75 and 0.92 which is satisfactory, but interviewer reliability only ranges between 0.34 and 0.73, indicating that some of subscales need to be improved. Concurrent validity is indicated by significant correlations (>0.50) between the ICF-related modules and the WHO Disability Assessment Schedule II (WHODAS II) and WHO Quality of Life brief version (WHOQOL-BREF) (Schippers, Broekman, Buchholz, Koeter, & Van Den Brink, 2010). A combination of the ten MATE modules can be used in an algorithm to determine the severity of the addiction, severity of other psychopathology, social disintegration and treatment history.

The modules to be used in the present study are:

Module 1 is an interview about substance use of the last month and the total years of regular use during life. The number of days the past month and the amount of use on an average day are asked about for alcohol, nicotine, cannabis, opiates, cocaine, stimulant drugs, XTC, other drugs, sedative medicines and gambling. For the rest of the interview, it is decided with the patient which is the main problem area. For every substance, excessive use can be calculated by specific criteria (e.g. more than 240 units of alcohol for the last month or more than one year of regular use and actual use of 28 out of 30 days for marihuana).

Module 4 contains of 11 binary questions (yes/no) about dependency and misuse of the problem area. Every 'yes' on question 2 to 9 and 11 (so without question 1 and 10) gets one point. The scoring range is 0 to 9. A score of 8 or more indicates a high severity.

Module Q1 contains of five questions about desire, based on a five point Likert-scale (score 0-4). The score of the five questions is added for the total score of this module (range 0-20). A score of 12 or more is an indication for a high severity.

A high severity of the addiction is a binary variable which is computed by following the algorithm below:

- 1) excessive use of three out of five substances in the last year (alcohol, nicotine, cannabis, opiates, cocaine / stimulant drugs) or,
- 2) A score of 8 or 9 out of 9 questions about dependency / misuse, or
- 3) A total score of 12 or more (range 0-20) on questions about desire

Objective 2:

SumID-Q is part of standard care for both departments (LVB-P and ORO). For the purpose of the validation of the TAPS-ID, patients are asked if they are voluntary willing to participate on the study by adding the TAPS-ID to the SumID-Q. Second, after completing the TAPS-ID and the SumID-Q, but before the scoring it, the assessor also rated the severity of the substance use problems on a five-point Likert scale by answering the following question: "I rate the addiction problem of the client as...". Possible answers were: absent, mild, moderate, severe, very severe.

Psychologists or psychiatric nurses are the assessors. They invite the patient for an appointment to take the SumID-Q. Participants were invited by telephone for the regular appointment that was scheduled at least one day later. During this telephone conversation, information was given about the validation study of the TAPS and patients were asked if they want to think about voluntarily participation. During the appointment, the information about the validation study was reviewed again, any additional questions from the patients were answered and when the patient agreed for participation, informed consent was signed. Patients signed informed consent to use the answers of the TAPS-ID and SumID-Q and background information (age, gender, diagnosis, medication) anonymously for this scientific purpose.

The answers from the TAPS-ID and SumID-Q are recorded on paper. Papers are stored in a locked closet at the department of care (GGZ or ORO).

To investigate research objective 2, the following measuring instruments are used:

SumID-Q:

The SumID-Q maps out what the client knows about psychoactive substances, what he/she knows, thinks about them, what is used in his/her environment, what he/she

may use and what the consequences of use and motivation are. to change. The structure of the interview makes it possible to discuss use in an open and pleasant way. It thus lays a foundation for any further diagnostics, interviews, interventions and preventive measures. The SumID-Q is designed to be administered to adults with a Slight Intellectual Disability, but also appears to be suitable for young people or people with a slightly lower or higher level. The SumID-Q can be administered by counselors and behavioral experts who have undergone training in the SumID-Q (Van der Nagel, Kiewik, De Jong, Van Dijk, Didden, 2011).

TAPS-ID:

The TAPS will be adapted for the target group of patients with MID. For this, pictures are added to the TAPS, questions are divided into sub-questions, and difficult words are replaced by a simpler alternative. We test the first version on several patients with ID and with various assessors. On basis of their recommendations, we make de definitive TAPS-ID.

This procedure was approved by the institutional scientific board named CWOI of the mental health care institute (GGZ Oost Brabant) and the Ethics Committee of Social Sciences of the Radboud University Nijmegen (number of approval: ECSW-2021-051).

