3. STUDY DESIGN

This is a descriptive study based on routinely collected data. The FACT teams that participate in the study work according to a care program in which screening and assessment are part of the standard care. This implies that since 2016, screening has been carried out at the start of treatment for: PTSD, a mild intellectual disability, addiction problems. The current screening for addiction problems is too limited and lacks a follow-up step in the form of structured assessment. In addition, at the start of treatment and annually in preparation of the treatment plan, the level of complaints is assessed by the care provider involved and the phase of recovery and the patient's quality of life are assessed. We want to use this data from patients in whom there is no suspicion of mild intellectual disability in anonymised form. In the research into the validity of the TAPS, we want to measure whether there is a relationship between the existence of problem substance use and a poorer treatment outcome (less decrease in complaints), and a reduced quality of life.

The TAPS has already been included as a replacement for the previously used screener for addiction problems by the various substantive advisory bodies that deal with the content and improvement of the care of the GGZ Oost Brabant.

In order to investigate the concurrent validity of the TAPS, a group of at least 40 patients will be asked permission to administer some parts of the MATE in addition to the TAPS.

The TAPS is too difficult for patients with intellectual disabilities. We therefore made adjustments to the translated TAPS (see below). The adjusted version for patients with ID is called the TAPS-ID. The validity of the TAPS-ID is examined by the comparison of the TAPS-ID and the SumID-Q (an instrument specially developed to map addiction problems in patients with MID). This will be carried out in a special department within secondary healthcare for patients with a combination of a severe mental disorder and intellectual disability (LVB-P) and in a healthcare setting for people with intellectual disabilities with minimal or light mental disorders (ORO). The SumID-Q is part of standard care for both departments. Trained employees who administer the SumID-Q also take the TAPS-ID.

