6. SAFETY REPORTING

6.1 Temporary halt for reasons of subject safety

This is not applicable because it is a retrospective observational study with one moment of data collection.

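### One unblinded assessor gives both screener and reference on one occasion, and the plan never says which comes first, so carry-over may bias the accuracy estimates

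*Combined protocol and SAP*

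**What the plan says.** **Objective 1 (section 5.3).** Psychologists or case managers give a routine battery that includes the TAPS. Screening for intellectual disability is done first, and then: "There was no fixed order for the other parts". The next paragraph describes what the validation study adds: "First, the assessor also took the parts of the MATE necessary to investigate the severity of the addiction". It gives the MATE modules no position relative to the TAPS.

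**Objective 2 (sections 3 and 5.3).** "Trained employees who administer the SumID-Q also take the TAPS-ID". Patients are invited for the SumID-Q and take part in the study "by adding the TAPS-ID to the SumID-Q". No order is given.

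**Occasion and blinding.** Section 6.1 calls this a "retrospective observational study with one moment of data collection". The section headed "5.2 Randomisation, blinding and treatment allocation" is answered as not applicable.

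**The only timing rule.** The assessor's five-point severity rating is made "after completing the TAPS and the MATE, but before the scoring of it", with a parallel rule for the TAPS-ID and SumID-Q. It governs the rating, not the order of the two instruments.

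**What depends on this.** Section 6.6 makes sensitivity, specificity and AUC the primary analysis. The Statistical Analysis section adds correlations with the reference for both goals, and a ROC-derived cut-off for the TAPS.

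**The concern.** An accuracy study needs screener and reference results that do not inform each other. Here two routes are open.

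- **Reference first.** The patient has already gone through his or her use with the same person before the screener starts. This matters most for objective 2. The SumID-Q takes 45-60 minutes (section 1) and is built to open up discussion of use. The TAPS-ID is wanted for patients in whom use is not yet suspected. A TAPS-ID taken after the SumID-Q is not being tested in that role, whatever the size of any bias.
- **Screener first.** The assessor who conducts the reference knows the screener answers. Scoring the MATE by algorithm does not fully protect it: the main problem area is agreed with the patient during the interview, and module 4 then asks about that area.

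At stake are the primary accuracy figures and the TAPS cut-off. If the order is not recorded, a reader cannot tell which route applied to which patient.

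**Working it through.** The documents give no order effect, so there is no plan figure to reproduce on this point. The steps below show what sizes are possible under stated assumptions.

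**Inputs from the documents.** TAPS-2 for alcohol: sensitivity (Se) 0.74, specificity (Sp) 0.79 (section 5.3, cited study). Sample: 40 required per group, stopping at 100 (section 4.4).

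**Assumed.** Share of results affected, c = 0.10, 0.25 or 0.50. Prevalence of reference-positives, 20-60%.

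**A. Reference first, disagreeing screener results pulled into line.** Se' = Se + c(1 - Se); Sp' = Sp + c(1 - Sp). Prevalence does not enter.

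| c | Se', Sp' if reference always first | Se', Sp' if reference first in half |
|---|---|---|
| 0.10 | 0.766, 0.811 | 0.753, 0.801 |
| 0.25 | 0.805, 0.843 | 0.773, 0.816 |
| 0.50 | 0.870, 0.895 | 0.805, 0.843 |

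Both figures rise because the model moves only disagreeing results. The upward direction is an assumption of the model, not a finding.

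**B. Reference first, more disclosure whatever the reference status.** Suppose a share c of screener negatives become positive. Se' = Se + c(1 - Se); Sp' = Sp(1 - c).

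- c = 0.10: Se' = 0.766, Sp' = 0.79 x 0.90 = 0.711. Youden index 0.477, against 0.74 + 0.79 - 1 = 0.53 at baseline.
- c = 0.25: Se' = 0.805, Sp' = 0.79 x 0.75 = 0.593. Youden index 0.398.

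This pattern is plausible for the MATE. Its reference is high severity: excessive use of three of five substances, or at least 8 of 9, or at least 12 of 20. TAPS-1 turns positive on any past-year tobacco or drug use. A user below the MATE threshold who discloses more becomes a false positive.

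**C. Screener first, reference pulled towards it.** With prevalence p, a share c of false positives become true positives and a share c of false negatives become true negatives. At p = 0.40 the cells are TP 0.296, FN 0.104, FP 0.126, TN 0.474.

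- c = 0.10: Se' = 0.3086/0.4022 = 0.767; Sp' = 0.4844/0.5978 = 0.810.
- c = 0.50: Se' = 0.359/0.411 = 0.873; Sp' = 0.526/0.589 = 0.893.

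So putting the screener first removes A and B by construction but leaves C open.

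**D. Could the data reveal it afterwards?** With N = 40 and 40% prevalence there are 16 reference-positives. The 95% Wilson interval around 0.74 is then 0.50 to 0.89, which covers the whole range in A. With N = 100 (40 positives) it is 0.59 to 0.85. If the order were split evenly, the approximate power to detect 0.74 against 0.87 among reference-positives (two-sided alpha 0.05, prevalence 20-60%) is 0.065 to 0.121 at N = 40 and 0.107 to 0.242 at N = 100. Randomising the order would therefore not give a useful test at these sizes.

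**The case against.** The strongest reply is that this is routine-care validation with an ordinary single-assessor limitation, and that more can be read into it than the text supports. Several parts of that reply stand.

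- A reader might infer that the plan declares the TAPS-MATE order free. It does not. The sentence about order closes the description of the routine battery, before the MATE is introduced, and says nothing about objective 2. The order against the reference is unspecified.
- A reader might infer that both references are long interviews. That is documented only for the SumID-Q. Three of ten MATE modules are used, their duration is not given, and the protocol summary puts the added burden at 15-20 minutes.
- For objective 1, flexible order within a wider battery is the intended setting, so the TAPS is not a stand-alone first test there. But the MATE modules are a study addition to that battery, so their position is for the study to set.
- Structured answers and algorithmic MATE scoring limit discretion in scoring. They do not stop one set of answers from influencing the other.
- Self-completion of the TAPS, left unread until the reference is recorded, may look like a full remedy, because section 5.3 describes the tool as one "which can be used as an interview or as a self-administered questionnaire" and reports similar diagnostic characteristics for both modes. That statement rests on a cited study of the TAPS, not the TAPS-ID, and self-completion departs from the described practice of completing the questionnaires together with the assessor.

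**Conclusion.** The gap is real: one assessor, one occasion, no blinding, and no rule or record of whether screener or reference comes first. Carry-over can therefore reach the primary accuracy estimates and the TAPS cut-off. For the TAPS-ID, a reference-first order would also fail to represent its use as a first screener.

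The stronger reading, that accuracy is overstated and that the bias is upward in either order, is not supported. Bias towards agreement is the likelier result when one person gives both instruments together, but the documents show neither presence, direction nor size. Calculation B lowers specificity under an equally simple assumption, and fatigue or the different look-back periods (past year and three months for the TAPS, last month for MATE module 1) could reduce agreement.

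The ranges of 0.77-0.87 for sensitivity and 0.81-0.90 for specificity rest on the assumed 10-50% share, the cited alcohol values and the reference always coming first. They show possible sizes only. Because the planned samples could not reveal such effects, prevention is preferable to later adjustment. This is a cheap improvement to the design, not a defect that invalidates the study.

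**What to change.** In section 5.3:

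1. State for objective 1 that the TAPS is always completed before the MATE modules, and for objective 2 that the TAPS-ID is always completed before the SumID-Q. The rest of the routine battery can stay flexible.
2. Add a field to the form recording the order actually used.
3. Section 5.3 is partly in the past tense and section 4.4 looks forward, so some patients may already have been assessed. For them, report the order used and accuracy by order where it is known, descriptively; where it is not known, say so.
4. State as a limitation that the assessor giving the reference still knows the screener answers. Fixing the order does not blind the assessor.

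The cost is one or two procedure sentences and one form field, with no extra staff or visit. The small downside is less flexibility within the appointment.

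### MATE high-severity variable: its first criterion needs a last-year window that Module 1 as described does not record, and its second can be met through gambling, which TAPS does not cover

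*Combined protocol and SAP*

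**What the plan says.** Section 5.3 (Study procedures) adds three MATE parts to the TAPS for objective 1: Module 1, Module 4 and module Q1. It combines them into a high-severity variable, the only MATE result that the protocol explicitly calls binary. Any one of three criteria is enough:

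1. "excessive use of three out of five substances in the last year", the five being alcohol, nicotine, cannabis, opiates and cocaine/stimulants;
2. "A score of 8 or 9 out of 9 questions about dependency / misuse" (Module 4);
3. a module Q1 (desire) total of at least 12 out of 20.

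On the data behind criterion 1, the section says: "Module 1 is an interview about substance use of the last month and the total years of regular use during life". It gives two examples of how excess is judged: "more than 240 units of alcohol for the last month" and, with more than a year of regular use, "actual use of 28 out of 30 days for marihuana".

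The Module 1 list ends with "other drugs, sedative medicines and gambling". The protocol continues: "For the rest of the interview, it is decided with the patient which is the main problem area". Module 4 then asks "about dependency and misuse of the problem area".

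The main endpoint (5.1.1) is problematic substance use. The Statistical analysis section relates TAPS to the degree of severity on the MATE and plans ROC analyses. Section 6.6 plans sensitivity, specificity and AUC, and names TAPS and MATE outcomes as the primary parameters for objective 1. The available text of 6.6 then breaks off.

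**The concern.** Two features of the definition matter if this variable serves as the reference for TAPS.

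First, criterion 1 and the data meant to feed it refer to different periods. A patient with excessive use earlier in the year but not in the last month is positive on one reading and negative on the other. An analyst would have to choose, and the published reference might not be the one that the protocol describes.

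Second, the definition allows a positive result for a problem that lies outside both the endpoint and the index test. A patient who is high severity only because of gambling would count against TAPS sensitivity if TAPS is negative. If TAPS is positive, the patient would count as a correct detection even though the reference result concerned something else. With at least 40 patients planned (section 3), single patients can move the estimates visibly.

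**Working it through.** **Scoring ranges (the plan's own figures).** Module 4 has 11 questions, of which 1 and 10 are not scored: 11 − 2 = 9, so the stated range of 0 to 9 is reproduced. Module Q1 has five questions scored 0 to 4: 5 × 4 = 20, so 0 to 20 is reproduced. The scoring is sound; the problem lies in the window and the scope.

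**Time windows, all from section 5.3.**

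| Element | Period |
|---|---|
| Criterion 1 | last year |
| Module 1, days and average amount | last month |
| Module 1, regular use | years over the lifetime, undated |
| Alcohol example | last month |
| Cannabis example | 28 of 30 days, plus more than one year of regular use |
| TAPS-1 | past year |
| TAPS-2 | last 3 months |

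The year in the cannabis example is a duration of regular use, not a 12-month recall period. Neither Module 4 nor module Q1 is described as recording amount or days of use. No described field therefore supplies last-year excess, and criterion 1 cannot be computed as worded.

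**Gambling route.**

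1. Gambling is on the Module 1 list.
2. The main problem area is agreed with the patient, and no area is excluded.
3. Module 4 is asked about that area only.
4. The three criteria are joined by *or*, so 8 or 9 on Module 4 suffices even when criterion 1 is not met.
5. TAPS-1 covers tobacco, alcohol, drugs and prescription medication. The TAPS-2 categories are likewise substances and medication.

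A patient can therefore be high severity for gambling. The text does not say which area module Q1 refers to; if it is the chosen area, criterion 3 has the same problem.

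**Illustration of one patient's weight (assumed inputs).** Assume that 20% to 60% of 40 patients are reference-positive, which gives 8 to 24. The percentages are the dual-diagnosis range in section 1, not a rate of MATE high severity. Assume an observed sensitivity of 0.75, close to the 0.74 that section 5.3 cites for problematic alcohol use against the CIDI. Now remove one gambling-only positive.

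- TAPS missed the patient: 6/8 = 75.0% becomes 6/7 = 85.7% (+10.7 points); 18/24 = 75.0% becomes 18/23 = 78.3% (+3.3).
- TAPS flagged the patient: 6/8 becomes 5/7 = 71.4% (−3.6); 18/24 becomes 17/23 = 73.9% (−1.1).

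At 100 patients, the stopping number in section 4.4, there would be 20 to 60 positives. A missed patient then moves 15/20 to 15/19 = 78.9% (+3.9) or 45/60 to 45/59 = 76.3% (+1.3).

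The sign depends on whether TAPS flags the patient. The documents do not say how often that would happen, or how often gambling would be the main area.

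**The case against.** The strongest reply is that the role of this variable is inferred. Module 4 and module Q1 each have their own high-severity cut-off, and excessive use is defined substance by substance, so other dichotomies are available. Section 6.6 speaks of accuracy for single items or combinations of items, which may mean substance-level comparisons that gambling would not affect. This stands. A reader might infer that the combined variable must be the reference; the documents make that plausible and no more.

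On the window, the mismatch may be a wording slip, and the MATE manual is in the reference list. That is possible, but the protocol does not show whether the criterion or the module description is wrong. The two statements still have to be reconciled.

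On gambling, nothing shows that such a patient will occur. The general MATE module list in 5.3 titles the dependence theme as concerning substances, which suggests a substance-only intent. It does not settle the matter: that list numbers dependence as 2 and gives number 4 to depression, anxiety and stress, while the scoring text for Module 4 speaks of the problem area and excludes nothing.

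It is also fair to say that any one misclassified patient among eight positives would have the same numerical effect, and that the inputs to the illustration do not describe MATE high severity. Both remarks stand, so the figures show only how much one patient weighs.

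A further inference to resist is that a gambling-primary patient tells us nothing about TAPS. Such a patient may also have a real substance problem, Module 1 still records their substance use, and a positive TAPS may be correct. The documents therefore do not support compulsory removal from the primary analysis.

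**Conclusion.** The point holds in two parts. Criterion 1 of the high-severity variable cannot be computed as worded from Module 1 as described; this is a contradiction within section 5.3. The stated rules also permit high severity on the basis of gambling alone; this follows from the text, but no sentence says that it is intended.

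The consequence for accuracy depends on the variable being used as the reference, which is not confirmed. A reader might conclude that TAPS sensitivity will be biased downwards. The documents do not support that, because neither the frequency of such patients nor their TAPS results can be known from them. The shift of about 3 to 11 points for one missed patient rests on the assumed 8 to 24 positives and the assumed sensitivity of 0.75; it is not an estimate of bias. No size can be given for the time-window discrepancy. The definition should be corrected before analysis, though the numerical effect may prove small or nil.

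**What to change.** - In 5.3, reconcile the criterion 1 window with the Module 1 data so that the rule uses a period that is actually recorded. Note how that period differs from TAPS-1 (past year) and TAPS-2 (last 3 months).
- Record the main problem area for each patient and state which area module Q1 refers to.
- Report the number of patients whose main area is gambling. Prespecify a sensitivity analysis of the accuracy results that leaves out all of them, whatever their reference result, so that the omission does not depend on the outcome.
- In 6.6, name the MATE variable that serves as the reference, unless the part missing from the available text already does so.

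The cost is wording in 5.3 and 6.6, confirmation that the main area is recorded, and one extra analysis on a slightly smaller sample. Each patient left out is 1/40 = 2.5% of the sample at the minimum size and 1/100 = 1% at the maximum. No new instrument is needed.
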